### 10.1.2 SAEs

Each AE is to be classified by the investigator as SERIOUS or NONSERIOUS. An AE that meets 1 or more of the following criteria/outcomes is classified as serious:

- Death
- Life-threatening
  - Life-threatening is defined as any event in which the subject was at risk of death at the time of the event; ‘life-threatening’ does not refer to an event which hypothetically might have caused death if it were more severe. For example, drug-induced hepatitis that resolved without evidence of hepatic failure would not be considered life threatening, even though drug-induced hepatitis of a more severe nature can be fatal.
- In-patient hospitalization or prolongation of existing hospitalization
  - Hospitalization is defined as an overnight admission with observation of a minimum of 24 hours. A hospitalization planned before the start of the study for a pre-existing condition that has not worsened during the AE reporting period does not constitute an SAE unless an untoward event occurs related to the procedure (e.g., elective hospitalization for a total knee replacement due to a preexisting condition of osteoarthritis of the knee that has not worsened during the course of the study).
- Persistent or significant disability/incapacity
  - Disability is defined as a substantial disruption in a person’s ability to conduct normal life functions.
- Congenital anomaly/birth defect
- Is considered a medically important event not meeting the above criteria, but which may jeopardize a subject, or may require medical or surgical intervention to prevent one of the criteria listed in this definition.

Serious also includes any other event that the investigator or sponsor judges to be serious. If there is any doubt whether the information constitutes an AE or SAE, the information is to be treated as an SAE.

In addition to the above criteria for classifying AEs as serious, the following situations will also be classified as serious for purposes of this study:

- Malignancies – Newly diagnosed malignancies or a recurrence of a malignancy will be reported as an SAE with the seriousness criterion “medically important” if no other seriousness criteria are met. If a subject develops basal cell carcinoma of skin, squamous cell carcinoma of skin, or cervical carcinoma in situ during the study, or has worsening of these events from baseline, the investigator will determine if the event is reported as an AE or SAE.
- Designated Medical Events – The sponsor maintains a list of Akebia specific designated medical events (DME) that they will always classify as SAEs. If an event on the DME list is reported as an AE, the investigator will be notified and additional information on the event (e.g., investigator confirmation of seriousness, causality) will be requested from the investigator. The DME list will be available upon request.

### **10.1.3 Adverse Events of Special Interest**

The following are considered to be AEs of special interest for this study:

- Malignancy (see [Section 10.1.2, SAEs](#))
- Elevation in ALT or AST >3 times ULN (see [Section 10.1.1, AEs](#))
- Pulmonary hypertension
- Pregnancy (see [Section 10.4, Exposure In-Utero](#))

Reporting and classification of these events as AEs (see Section 10.1.1, AEs) or SAEs (see Section 10.1.2, SAEs) will be as per investigator decision.

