### **10.3 Reporting**

Each AE is to be classified by the investigator as SERIOUS or NONSERIOUS based on the criteria in Section 10.1.2, SAEs.

All AEs that occur in study subjects during the AE reporting period specified in this protocol will be reported, whether or not the event is considered related to study drug (vadadustat or epoetin alfa).

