#### **10.3.2 Reporting AEs**

NONSERIOUS AEs are to be reported on the AE CRFs.

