#### **10.3.3 Reporting SAEs**

Any SAE, regardless of causal relationship, will be reported to the sponsor's Medical Monitor or CRO designee within 24 hours after the investigator becomes aware of the SAE. Compliance with this time requirement is essential so that the sponsor may comply with its regulatory obligations.

The initial SAE report should be completed as fully as possible but will contain, at a minimum items number 1 to 6:

1. Subject number/ID, sex, and age/date of birth
2. The date of report
3. Name of the reporter
4. Name of the suspected medicinal product

5. A description of the event, including event term(s), seriousness criteria, and a clinical summary of the event
6. Causality assessment

If the causality assessment is not provided in the initial report an updated report with the causality must be provided within 24 hours, once assessed.

Information about all SAEs (either initial or follow-up information) will be collected and recorded in English on the electronic SAE Report Form within the EDC system. The investigator will assess the relationship to each specific component of the study treatment. If the event meets serious criteria and it is not possible to access the EDC system, a paper SAE Report Form will be sent to the CRO via email or fax, or the investigator will call the CRO SAE hotline within 24 hours of being made aware of the SAE (reference the site manual for contact information). When the EDC system becomes available again, the SAE information will be entered within 24 hours of the system becoming available.

The investigator will report follow-up information relating to an SAE to the sponsor's Medical Monitor or CRO designee within 24 hours of awareness updating the electronic CRF with the new information or by submitting a paper SAE Report Form in the event that the EDC is not available. When the EDC system becomes available, the SAE information will be entered within 24 hours. The subject will be observed and monitored carefully until the condition resolves or stabilizes.

All deaths are to be thoroughly investigated and reported. Autopsy reports and death certificates are to be obtained, if possible.

The sponsor and/or its designee are responsible for reporting SAEs to all applicable regulatory agencies and the central ethics committees within the required timeline.

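### Section 10.1.3 lets the investigator decide whether a malignancy is an SAE, against 10.1.2, and the work-up for ALT/AST above 3x ULN omits the eosinophil count that Table 2 needs

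*Protocol*

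**What the plan says.** **Classification of special-interest events.** Section 10.1.3 names four event types: malignancy, ALT or AST above 3x ULN, pulmonary hypertension and pregnancy. It ends: "Reporting and classification of these events as AEs (see Section 10.1.1, AEs) or SAEs (see Section 10.1.2, SAEs) will be as per investigator decision".

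Section 10.1.2 has a list introduced by the statement that "the following situations will also be classified as serious for purposes of this study". Its first entry reads: "Newly diagnosed malignancies or a recurrence of a malignancy will be reported as an SAE with the seriousness criterion" of medical importance, if no other criterion applies. For basal cell carcinoma of skin, squamous cell carcinoma of skin and cervical carcinoma in situ only, "the investigator will determine if the event is reported as an AE or SAE". The second entry says the sponsor keeps a list of "designated medical events (DME) that they will always classify as SAEs". The contents of that list are not given.

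Section 10.1.1 directs that a new ALT or AST elevation above 3x ULN be reported as an SAE within 24 hours if its conditions are met. The second of those conditions does not appear in the text at hand.

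On routing, Section 10.3 says: "Each AE is to be classified by the investigator as SERIOUS or NONSERIOUS based on the criteria in Section 10.1.2, SAEs". Section 10.3.2 says: "NONSERIOUS AEs are to be reported on the AE CRFs". Section 10.3.3 sends SAEs to the sponsor's "Medical Monitor or CRO designee within 24 hours after the investigator becomes aware of the SAE".

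**Liver stopping rules.** Table 2 in Section 9.4 has five criteria for permanent discontinuation. The fifth is ALT or AST above 3x ULN accompanied by symptoms or by eosinophilia. Section 10.1.1 offers a temporary stop, with later resumption, only to subjects who meet no Table 2 criterion.

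**The concern.** A malignancy that is neither fatal nor life-threatening and needs no admission is the kind of event that the mandatory rule in 10.1.2 exists to catch. If the closing sentence of 10.1.3 is taken at its word, the site may call it nonserious. It then goes on the AE CRF, and the site has no 24-hour duty to report it.

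The second part has the same character: a safety rule that the protocol's other instructions do not support. Whether a subject with ALT/AST above 3x ULN takes the temporary or the permanent path depends in part on eosinophil status, but nothing requires that status to be measured. Section 4.3 names hepatotoxicity as an important potential risk, and Section 4.2 says that 750 and 900 mg are being given to dialysis patients for the first time.

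**Working it through.** No sample size, power or error rate is involved. The check compares the texts and counts.

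**1. Special-interest events against the mandatory SAE rules**

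| Event in 10.1.3 | Rule elsewhere | Conflict with investigator discretion |
|---|---|---|
| Malignancy | 10.1.2: SAE, except three named carcinomas | Yes, outside those three |
| ALT/AST above 3x ULN | 10.1.1: SAE if all its conditions hold | Only when they all hold; one is not visible |
| Pulmonary hypertension | No specific SAE rule found | None found |
| Pregnancy | 10.4: not an AE in itself; certain outcomes are SAEs | Not counted |

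So 1 of 4 event types is in a fully visible conflict and a second is in a conditional one. The narrow exception in 10.1.2 is informative: it would have no purpose if discretion applied to every malignancy.

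**2. Tests ordered after ALT/AST above 3x ULN**

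- Section 10.1.1, repeat within 48 to 72 hours: ALT, AST, ALP, total bilirubin = 4.
- Appendix A, footnote [s], from the Unscheduled Visit kit: INR, PT, aPTT = 3.
- Total: 4 + 3 = 7, of which eosinophil counts = 0.

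**3. Could a scheduled test fill the gap?**

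- Under Section 9.2.2, LFT visits during dosing after Day 1 are Visits 3, 4, 5, 6, 7, 9, 11, 12 and 13 = 9.
- Under Section 9.2.2 and footnotes [o] and [q], a CBC with differential is done at Day 1 and Visit 14 only. Overlap with those 9 visits = 0.
- The two scheduled differentials are 141 − 1 = 140 days apart, give or take the 3-day window at Visit 14.
- A subject stopped permanently has the Visit 14 assessments early, but that differential comes after the decision it should inform.

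**4. Comparison with INR**

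INR is also a Table 2 input that is not on the visit schedule. Footnote [s] deals with this by making its collection mandatory after any elevation above 3x ULN. Eosinophilia is in the same position in Table 2 and has no such instruction.

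**5. Path followed as written**

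Take an asymptomatic subject with ALT above 3x ULN, bilirubin and INR below their Table 2 limits, and eosinophilia that nobody has measured. No Table 2 criterion is seen to be met, so the temporary stop applies and drug may restart once values resolve or stabilize. Table 2 requires a permanent stop for this subject.

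**The case against.** **On malignancy.** Every AE in this trial is classified by the investigator, so the closing sentence of 10.1.3 may mean only that special-interest status does not by itself make an event serious. The sentence and the malignancy bullet both point to 10.1.2, Section 10.3 says to classify by the 10.1.2 criteria, and 10.1.2 resolves doubt towards SAE. The sponsor may also judge an event serious, its designated-events list may cover malignancy, and Section 10.6 provides regular review of safety data. These safeguards make a wrong classification less likely and easier to correct. They do not make the two rules agree. The doubt clause helps only a site that is in doubt, and the designated-events check acts only after the event has been entered as an AE.

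**On ALT/AST.** Because the second condition in 10.1.1 cannot be read, it may itself call for investigator judgement. That is a fair limit, and this part is claimed only for elevations that meet every condition.

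**On eosinophilia.** An investigator using the temporary path must in principle establish that no Table 2 criterion is met, and Section 9.3.6 makes the differential available through the Unscheduled Visit kit. Drug is stopped on either path, so the exposure arises only on resumption. All of this is correct. What remains is that the test is optional where the parallel INR test is compulsory.

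**On weight.** No efficacy endpoint or analysis is touched, and Section 11.7 summarises special-interest AEs whatever their SAE status. This limits the importance of the point but does not remove it.

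**Conclusion.** The point holds. Section 10.1.3 contradicts 10.1.2 on malignancy outside the three named carcinomas. It contradicts 10.1.1 on ALT/AST above 3x ULN only where all the SAE conditions of that section are met, and this half stays conditional on text that is not at hand. The consequence is a possible missed 24-hour report from the site, with partial backstops.

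The eosinophilia gap affects one limb of one of the five Table 2 criteria. It matters for asymptomatic subjects, since symptoms would trigger the stop without any blood count, and it rests on the investigator not ordering an available test. It is better described as an inexpensive improvement than as an error.

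The protocol gives no expected rate of malignancy or of ALT/AST above 3x ULN, so the number of subjects affected cannot be stated. Both items concern safety conduct and reporting and should be fixed.

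**What to change.** 1. In Section 10.1.3, keep the closing sentence but add at its end: *except where Section 10.1.1 or 10.1.2 requires SAE reporting*. This restores the mandatory rules and leaves discretion where those sections allow it.
2. In Section 10.1.1 and Appendix A footnote [s], add a CBC with differential to the tests required after ALT or AST above 3x ULN, and require the result to be checked against Table 2 before study drug is resumed.

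The cost is amendment wording plus one extra blood count in subjects with such an elevation. The test is already in the Unscheduled Visit kits, so no new supply is needed.

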### **10.2 Eliciting AE Information**

The investigator is to report all directly observed AEs and all AEs spontaneously reported by the study subject. In addition, each study subject will be questioned about AEs at each visit following randomization.

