## 5 STUDY OBJECTIVES AND ENDPOINTS

### 5.1 Primary Objective

To assess the efficacy and safety of daily dosing of vadadustat compared to epoetin alfa for 12 weeks in hemodialysis subjects.

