#### **8.4.11 Treatment Compliance**

Throughout the study, subjects in the vadadustat arm will be guided regarding dosing compliance using an eDiary or paper dosing reminders. The focus of the vadadustat eDiary is to guide subjects to remind them of the dose, instruct them to hold their dose for the PK/PD sample dates and guide them if they have transitioned from daily dosing to TIW dosing. Subjects will also be questioned at study visits on whether they have questions or have experienced any problems related to the dosing of vadadustat. The investigator will also maintain drug accountability logs itemizing all study drugs dispensed to and returned from each subject during the study.

Treatment compliance will be determined from these logs, subject questioning, and the study drug Case Report Form (CRF).

For epoetin alfa, the dose that is administered is required to be entered in the electronic data capture (EDC) system, and the EDC system will be used to determine dosing compliance.

Subjects who miss doses will be counseled on the importance of compliance.

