- **Vital Sign Measurements**: Vital signs will include temperature, heart rate (HR), BP, respiratory rate (RR), and dry weight. Temperature, HR, BP, and RR will be assessed in the seated position after 5 minutes of rest. For BP, a total of two measurements at intervals of at least 2 minutes should be performed. Temperature, HR, BP, and RR will be collected at SV1, SV2, Baseline/Day 1, during all study visits, and Visit 14 (EOT). Measurements will be taken prior to blood draws when possible.  
Dry weight will be collected for all subjects at SV2, Baseline/Day 1, Visit 9 and 14 (EOT). For subjects on epoetin alfa, subjects will be weighed for dosing as per the local standard of care.
- **12-Lead ECG**: A standard 12-lead ECG will be performed at Baseline/Day 1, which may be obtained up to 3 days prior to Baseline/Day 1. The ECG will be obtained after the subject has been resting comfortably in a supine position for approximately 5 minutes and will be taken prior to vital sign assessments and blood draws when possible. All ECGs will be reviewed by the investigator for the presence of rhythms of potential clinical concern. A record of the tracing(s) will be made and retained with other source documents.
- **AE Assessments**: AE collection will begin from time of randomization through study end (Follow-Up Visit). The investigator and study personnel will review each subject's laboratory and clinical evaluation findings and query the subject directly regarding AEs (see [Section 10](#), Adverse Events). Subjects must be followed for AEs until the final required protocol visit (study end date) or until all drug-related toxicities and SAEs have resolved (or are considered chronic/stable), whichever is later.
- **Prior and Concomitant Medication Recording**: All prior and concomitant medications (except those routinely administered as part of the hemodialysis procedures, such as heparin or saline flushes used for routine catheter maintenance, unless relevant for an AE or SAE) taken within 30 days prior to Baseline/Day 1 and through the final study visit will be recorded on the appropriate CRF.

Iron treatment regimen 30 days prior to Baseline/Day 1 and through the final study visit will be recorded on the appropriate CRF. In addition, to ensure adequate collection of prior ESA dosing history, a minimum of 8 weeks of ESA therapy prior to start of study drug will be recorded on the appropriate CRF page.

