### **9.3.2 Baseline/Day 1 (Visit 1)**

Epoetin alfa dosing will have been stopped for a minimum of 5 days in the Main study or 2 days in the ESA hyporesponder parallel study until Baseline/Day 1.

On Baseline/Day 1, blood sample collection and other Baseline/Day 1 procedures will be completed prior to dosing with study drug (vadadustat or epoetin alfa). On Baseline/Day 1, study drug will be administered at the study site, and will be administered after the PK sample is collected and prior to the dialysis session.

At Baseline/Day 1, the following activities/procedures will be performed:

- Review of study eligibility criteria
- Review of acceptable methods of contraception
- Review of medical history for new conditions since SV2
- Review of medication use since SV2
- Randomization
- Introduction to and instruction on the use of the eDiary and paper dosing reminders
- SF-36v2, PGI-S, and EQ-5D-5L assessments
- Abbreviated, symptom-directed physical examination, at the discretion of the investigator, as clinically indicated
- 12-lead ECG: ECGs will be completed prior to blood draws when possible and will be obtained after the subject has been resting supine comfortably for approximately 5 minutes; ECG may be completed and reviewed by the investigator on Baseline/Day 1 or if needed for scheduling reasons (e.g., dialysis treatment is scheduled for early morning of Baseline/Day 1), the ECG can be completed and reviewed up to 1-3 days prior to Baseline/Day 1.
- Vital signs including temperature, HR, BP, and RR (assessed in seated position after 5 minutes of rest and prior to blood draws), and dry weight

- Laboratory Procedures:
  - CBC (including differential)
  - Reticulocyte count
  - CRP
  - Serum chemistry
  - LFTs
  - Iron indices
  - Lipid profile
  - Biomarkers (VEGF, and Hepcidin)
  - PK prior to vadadustat or epoetin alfa dosing (see [Section 9.2.2.1](#), PK/PD Sampling for Subjects Randomized to Vadadustat and [Section 9.2.2.2](#), PK Sampling for Subjects Randomized to Epoetin Alfa) and prior to the dialysis session
- Study drug assessments and procedures:
  - Subject will take/receive their first dose of study drug at the study site during Baseline/Day 1
  - For subjects in the vadadustat treatment arm only:
    - Initiate vadadustat dosing
    - Vadadustat drug dispensation
    - Review vadadustat dosing instructions
  - Epoetin alfa dosing will continue for the subjects in the epoetin alfa arm

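### Section 8.4.11 asks only vadadustat subjects about dosing problems, with no epoetin alfa counterpart; in an open-label trial this could prompt mild AE reports unevenly

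*Protocol*

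**What the plan says.** Formal AE elicitation is the same in both arms. Section 10.2 states that "each study subject will be questioned about AEs at each visit following randomization". Section 9.2.1 has staff review findings and "query the subject directly regarding AEs". The AE review row of Appendix A is not split by arm, and the status checks in weeks without a visit (9.1.4) apply to everyone. Section 10.3 requires every AE to be reported for either drug, related or not.

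Section 8.4.11 then adds, within its account of vadadustat compliance: "Subjects will also be questioned at study visits on whether they have questions or have experienced any problems related to the dosing of vadadustat". It names subject questioning, with the accountability logs and the study drug CRF, as a source for judging compliance. For epoetin alfa the doses given are entered electronically and "the EDC system will be used to determine dosing compliance"; no question to the subject is stated.

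The visit lists in 9.3.2 and 9.3.3 carry a block headed "For subjects in the vadadustat treatment arm only". In 9.3.3 it covers bottle registration, dispensing, dosing instructions, compliance and reconciliation. AE review is listed separately, for all subjects.

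The study is open-label (8.4.2). The primary objective is comparative on safety as well as efficacy: "To assess the efficacy and safety of daily dosing of vadadustat compared to epoetin alfa for 12 weeks in hemodialysis subjects". Section 11.7 summarizes AEs, including those the investigator judges related, by treatment group, descriptively.

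**The concern.** One arm receives a second, drug-directed invitation to mention problems and the other does not. Section 10.1.1 defines an AE as any untoward medical occurrence in the reporting period, and nothing in 8.4.11 keeps answers to the compliance question apart from AE recording. A subject who replies that the tablets cause nausea has reported an AE.

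The events most open to this are mild and subject-reported. Section 4.3 lists nausea, diarrhea, vomiting, headache and abdominal pain among the identified risks of vadadustat. Tolerability is also of particular interest here, because the protocol describes this as the first study of 750 and 900 mg in dialysis-dependent subjects (4.2, 6.3). A complaint raised in answer to a question naming vadadustat may also be more readily classed as related by an unblinded investigator. A descriptive analysis gives no protection, because the tabulated rates are themselves the result.

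**Working it through.** **1. Comparison of the provisions**

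| Element | Vadadustat | Epoetin alfa |
|---|---|---|
| AE question at each visit (10.2, 9.2.1) | yes | yes |
| Status checks in other weeks (9.1.4) | yes | yes |
| Duty to report all AEs (10.3) | yes | yes |
| Question on dosing problems (8.4.11) | yes | none stated |
| Compliance source (8.4.11) | logs, subject questioning, CRF | electronic dose entries |

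The only arm difference in what subjects are asked about problems is the fourth row.

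**2. Order of questions**

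Sections 9.3.3 and 9.3.4 list AE review before the medication procedures, while 9.3.2 lists it after them. None says that the order of the list is the order of conduct. The protocol therefore does not ensure that the common question comes first.

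**3. Planned comparison sizes**

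From section 11.1 and the ratios in 8.4.1:
- Low-dose group: 40 split 3:3:2 gives 15, 15 and 10.
- High-dose group: 55 split 3:3:3:2 gives 15, 15, 15 and 10.
- Main study: 5 × 15 = 75 vadadustat and 10 + 10 = 20 epoetin alfa.
- Hyporesponder study: 30 split 1:1 gives 15 and 15.

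The synopsis says the two studies are analyzed separately, so these are the relevant bases. They exclude the optional enrollment increase.

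**4. Illustration of size**

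The protocol gives no figure to reproduce, so both inputs are assumed:
- p, the AE incidence, the same in both arms: 30% to 70%.
- e, the extra share of events recorded on vadadustat because of the prompt: 0 to 10%.

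Shift in the recorded difference = p × e. For scale, the 95% half-width is 1.96 × √[p(1−p)(1/n₁ + 1/n₂)], a rough normal approximation at these sizes. All results are in percentage points.

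| p | e = 0 | e = 2% | e = 5% | e = 10% | Half-width, 75 v 20 | Half-width, 15 v 15 |
|---|---|---|---|---|---|---|
| 30% | 0 | 0.6 | 1.5 | 3.0 | 22.6 | 32.8 |
| 50% | 0 | 1.0 | 2.5 | 5.0 | 24.7 | 35.8 |
| 70% | 0 | 1.4 | 3.5 | 7.0 | 22.6 | 32.8 |

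Example at p = 50%, 75 versus 20: 1.96 × √[0.25 × (1/75 + 1/20)] = 24.7 points. The largest shift, 7.0 points, is 0.07 × 75 ≈ 5 vadadustat subjects in the Main study and 0.07 × 15 ≈ 1 in the hyporesponder study.

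**The case against.** The strongest reply is that 8.4.11 is not about AEs. Its question concerns dosing, its stated use is to judge compliance, and the surrounding text covers reminders, held doses, the switch to three-times-weekly dosing and counseling on missed doses. Vadadustat is taken at home, whereas epoetin alfa is given at the clinic, so a compliance question is needed in one arm only. A forgotten tablet is not in itself an AE. A genuine symptom should already have surfaced under the direct AE question put to every subject at every visit, so the added yield may be nil. The vadadustat-only block in the visit lists contains no AE elicitation.

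Most of this stands. Section 10.2 is sound as written, the route of administration explains an arm-specific compliance check, and the extra yield may indeed be zero. What it does not explain is why the question extends to any problems related to dosing rather than to missed doses and instructions, or why no order relative to the AE question is fixed. A symptom mentioned at that point must still be reported.

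**Conclusion.** The point holds as a minor one. A subject-directed question about dosing problems is written for one arm of an open-label trial with a comparative safety objective. It could produce some differential ascertainment of mild, subject-reported AEs and of related AEs. Hb excursions and laboratory values do not depend on it.

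A reader might infer more: that AEs are solicited harder on vadadustat and the safety comparison is biased. The documents do not support that. AE elicitation proper is the same in both arms, and the size of any effect cannot be derived from the protocol.

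A reader might also attach a large figure. Suppose 20% of both arms would report such a complaint, and the prompt multiplies reporting on vadadustat by 1.25 to 2. The table would then show 25% to 40% against 20%, a false difference of 5 to 20 points, or 4.5 to 18 extra subjects among all 90 vadadustat subjects. Neither input is in the documents, and the multiplier excludes 1, so that figure assumes the effect it claims to show. Pooling 90 versus 35 also combines two studies that are to be analyzed separately. On the same assumptions the excess would be 3.75 to 15 of 75 and 0.75 to 3 of 15.

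The 0 to 7.0 points in the illustration also rest on assumed inputs. They show only that a modest effect would be small beside sampling error in a trial of this size.

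**What to change.** Amend 10.2 and 8.4.11 to state that the common AE question is asked first, in the same words in both arms, before any arm-specific review of tablets, compliance or dosing instructions. Then choose one of two options:

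- ask both arms the same drug-neutral follow-up, such as whether they have had any problems with their study treatment; or
- limit the vadadustat-only question to missed doses and understanding of the dosing instructions.

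The first option adds one short question per visit for about 35 epoetin alfa subjects (20 + 15) and may slightly raise the reported AE rate in that arm. The second adds nothing. Neither needs more staff, visits or procedures.
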